2.2 Risk/Benefit assessment

risk assessment:

This study was an observational one, and the core intervention was only a single venous blood sample collection of 3mL (approximately 1ml of serum). This operation

is a routine and mature medical practice in clinical practice, with extremely low and controllable risks.

Benefit evaluation:

Cancer patients: They will not receive immediate individualized diagnosis or treatment recommendations from this study. However, the data it contributes will drive the development of better tumor markers, which may benefit its future disease management (such as more precise follow-up monitoring).

Healthy control subjects: Contribute to establishing baseline standard values for healthy populations and promote public health. After the research is completed and the method is mature, the baseline data in which it participated may provide a reference background for its own future similar screening.

三、 Research objectives and endpoints

3.1 objective

3.1.1 main purpose

To evaluate the differences in serum histone succinylation between malignant solid tumors and healthy individuals, in order to verify its early screening value.

3.1.2 secondary objective

To clarify the correlation between histone succinylation modification in serum and different types of tumors and tumor stages, and to statistically analyze the correlation between histone succinylation in serum and therapeutic effects (including surgical treatment, radiotherapy, and systemic therapy) as well as clinicopathology.

3.2 evaluation index

The evaluation indicators are: the sensitivity, specificity, positive predictive value, negative predictive value of the serum histone succinylation screening method, and the predictive value of the Youden index (early diagnosis, therapeutic effect evaluation and prognosis).

四、 study population

4.1 inclusion criteria

case group

- 1) ≥ 18 years old, gender not limited;
- 2) Malignant solid tumors diagnosed by cytology or histology require subsequent anti-tumor treatment (systemic therapy, radical or concurrent chemoradiotherapy/radiotherapy, or surgical treatment).

control group

- 1) ≥ 18 years old, gender not limited;
- 2) Non-tumor patients undergoing health check-ups;

4.2 exclusion criteria

- 1) Pregnant women
- 2) Those with severe mental disorders or language communication disorders;
- 3) Other circumstances where the researcher deems it unsuitable to participate in this study.

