5.2.2 Research flowchart

5.2.3 Blood collection process table

grouping								
	Screening period							
healthy person	D-7—D0							
Cancer patients are receiving systemic treatment		Chemotherapy cycle						
		C1D1	C2	C3	C4	C5	C6	
	D-7—D0			D1± 3		D1±3		
Cancer patients who receive radical chemoradiotherapy/radiotherapy	D-7—D0	After the completion of radiotherapy/chemoradiotherapy		Four to six weeks after the completion of radiotherapy/chemoradiotherapy				
		D _{end} D _{end} +3		On the day of follow-up				
A tumor patient undergoing surgery	D-7—D0	postoperation	Postoperative discharge day/the day before discharge					
	D1—D3							

5.3 statistic analysis

This study adopted a mismatched case-control study (500 cases in the case group and 500 cases in the healthy control group). The sample size was determined based on the effect size of the previous pre-experiment (Cohen's $d=1.2$) and considering a 10% dropout rate. All statistical analyses were performed using R, with a test level of $\alpha=0.05$. Main analysis 1) Comparison of histone succinylation levels between groups - After Shapiro-Wilk normality and Levene homogeneity of variance tests, independent sample t-tests (conforming to normal distribution) or Mann-Whitney U tests (non-normal data) were selected. Report mean difference (MD)/median difference and 95% confidence interval (CI), Cohen's d effect size; 2) Diagnostic

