efficacy evaluation - Calculate the area under the curve (AUC) and its Bootstrap 95% CI through the ROC curve, and determine the optimal cut-off value by maximizing the Youden index. And calculate the sensitivity, specificity, positive predictive value (PPV), negative predictive value (NPV), and their exact Clopper-Pearson 95% CI. Secondary analysis: 1) Subgroup correlation - One-way analysis of variance (ANOVA) or Kruskal-Wallis test was used to compare the level differences among different tumor types (Bonferroni-adjusted post hoc test), and Cuzick's trend test was used to analyze the ordered association of TNM stages; 2) Therapeutic effect evaluation - The level changes before and after treatment were evaluated using paired t-test /Wilcoxon signed-rank test; 3) Prognostic value - The baseline succinylation level (median grouping) was included in the Cox proportional hazards model. After adjusting for age, stage, and treatment regimen, the hazard ratio (HR) and 95% confidence interval (CI) were calculated. The survival curve was plotted using the Kaplan-Meier method (Log-rank test). Multivariate analysis: A Logistic regression model was constructed (including succinylation level and covariates such as age and gender). AUC was compared by DeLong test, goodness-of-fit was evaluated by Hosmer-Lemeshow calibration curve, and clinical net benefit was analyzed by decision curve (DCA). If multi-site modifications are detected, LASSO regression is used to screen biomarker combinations. Quality control: Grubbs test /Winsorize for outliers, multiple imputation (MICE) for filling <5% of missing covariates. Sensitivity analysis: Robustness was verified by excluding stage I tumors, and the 70%-30% dataset was split for cutoff value training - validation. All multiple comparisons were controlled for the false discovery rate (FDR) using the Benjamini-Hochberg method.

六、Ethical requirements

Clinical research will comply with relevant regulations such as the Declaration of Helsinki of the World Medical Congress. The research can only be implemented after it has been approved by the ethics committee before it commences.

Before each subject is enrolled in this study, the researcher is responsible for providing the subject or their agent with a complete and comprehensive introduction

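### The planned stage trend test and tumour-type comparison each take one factor, so if tumour types differ in stage mix, neither can separate type from stage

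*Protocol*

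**What the plan says.** Secondary analysis 1 in Protocol section 5.3 names two tests on the cases. For tumour type, "One-way analysis of variance (ANOVA) or Kruskal-Wallis test was used to compare the level differences among different tumor types", with Bonferroni-adjusted post hoc comparisons. For stage, "Cuzick's trend test was used to analyze the ordered association of TNM stages". No stratification or covariate is stated for either.

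These tests serve the secondary objective in section 3.1.2, to "clarify the correlation between histone succinylation modification in serum and different types of tumors and tumor stages". Objective 2 in section 2.1.2 goes further: it wants to know both whether the marker tells tumour types apart and whether it reflects disease progression.

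The case group is broad. Section 4.1 admits "Malignant solid tumors diagnosed by cytology or histology require subsequent anti-tumor treatment", and section 5.3 plans "500 cases in the case group and 500 cases in the healthy control group". No quota by type or stage is set.

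No other analysis stated in section 5.3 separates the two factors. The Cox model adjusts for age, stage and treatment regimen but not type, and concerns prognosis. The logistic model names age and gender as covariates. Leaving out stage I tumours is a robustness check. Bonferroni and false-discovery-rate control deal with multiplicity, not with confounding.

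**The concern.** Cuzick's test takes one ordered factor, and one-way ANOVA or Kruskal-Wallis takes one grouping factor. Applied to a mixed set of solid tumours, each absorbs whatever the other factor contributes, as far as the two are associated.

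This can go wrong in three ways, each needing two conditions:

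- **False stage trend:** types differ in stage mix, and types differ in marker level.
- **Hidden stage trend:** as above, with the later-presenting types having the lower levels.
- **False type difference:** types differ in stage mix, and the marker varies with stage.

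The second condition in each case is one of the very effects that the secondary objective sets out to find, so it is not remote. At stake is the reading of the result: a reported stage trend might be a type effect, a reported type difference might be a stage effect, and the planned output could not tell which.

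**Working it through.** **The plan's own figure.** The protocol gives none for this analysis. Its only sample-size figure, 500 per group from Cohen's d = 1.2 and 10% dropout, concerns cases against controls and does not bear on this point.

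**Inputs from section 5.3.** 500 cases and a test level of 0.05, taken as two-sided because sidedness is not stated.

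**Assumed inputs.** Stage mixes by type, level differences between types, and the size of any stage effect. The protocol gives none of these, so they are varied.

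**Step 1: why the pooled test picks up type.** Suppose there is no stage effect within any type. With type means μ_k and mean stages s_k, the pooled covariance of level and stage is then cov(μ_k, s_k). It is zero if all types share the same mean stage or the same level. With a within-type SD of 1, the trend statistic is centred near z = √500 × cov / √[var(stage) × (1 + var(μ))].

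Take five equal types whose means are equally spaced over 0.5 SD (−0.25, −0.125, 0, 0.125, 0.25), so var(μ) = 0.03125.

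- *Moderate mix* (stage IV from 15% to 35% across types): mean stages 2.15, 2.32, 2.50, 2.68, 2.85; var(stage) = 1.25. cov = 2 × (0.25 × 0.35 + 0.125 × 0.18) / 5 = 0.044. z = 22.36 × 0.044 / √(1.25 × 1.03125) = 0.87. Chance of |Z| > 1.96: about 14%.
- *Strong mix* (stage IV from 5% to 50%): mean stages 1.75, 2.15, 2.50, 2.85, 3.25; var(stage) = 1.29. cov = 2 × (0.25 × 0.75 + 0.125 × 0.35) / 5 = 0.0925. z = 22.36 × 0.0925 / √(1.29 × 1.03125) = 1.79. Chance: about 43%.

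**Step 2: simulation of the same five-type settings (4000 trials each).** This gives 13% and 42%, in line with step 1.

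| Stage mix | Range of type means, no stage effect | Pooled Cuzick | Stratified by type | Stage I-to-IV shift, no type effect | Kruskal-Wallis by type | Type adjusted for stage |
|---|---|---|---|---|---|---|
| Same in all types | 0.5 / 1.0 SD | 5% / 6% | 5% / 6% | 0.5 / 1.0 SD | 5% / 5% | 6% / 5% |
| Moderate | 0.5 / 1.0 SD | 13% / 38% | 4% / 5% | 0.5 / 1.0 SD | 9% / 24% | 5% / 5% |
| Strong | 0.5 / 1.0 SD | 42% / 92% | 5% / 5% | 0.5 / 1.0 SD | 28% / 85% | 5% / 4% |

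The first row shows that with equal stage mixes neither test misleads.

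**Step 3: eight types of unequal size, varying the stage-mix difference.** Strong means stage I-IV mixes from 40/35/15/10% to 5/15/30/50% across types; moderate is half that spread and small a quarter. For the trend test there is no stage effect within type, and the between-type SD is 0.3 to 0.5. For the type test there is a stage effect only, 0.3 SD per stage.

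| Stage-mix difference | Pooled Cuzick significant | One-way type test significant |
|---|---|---|
| Small | 6-14% | 6% |
| Moderate | 7-45% | 12% |
| Strong | 15-96% | 42% |

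Stratified by type, or adjusted for stage, the figures are about 5%. The low end of each Cuzick range has type levels unrelated to stage mix; the high end has later-presenting types higher. The top of the strong range depends heavily on how closely level and stage mix line up: other ways of setting this up gave 73% to 91%.

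**Step 4: masking.** With a true trend within types and later-presenting types lower, at the strong stage-mix difference, pooled power fell to 26% against 92% stratified. A separate run with 0.15 SD per stage gave 45% (between-type SD 0.3) or 19% (0.5), against 94% with type in the model.

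**Step 5: price of stratifying.** In the five-type settings with unequal mixes, power for a true 0.5 SD shift from stage I to IV is 95.0-97.5% stratified, against 98.2-98.4% pooled.

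**The case against.** Five points can be made for the plan.

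1. *The documents do not show that the conditions hold.* No stage mix is given, the pilot listing (Figure 3) has no stage column, and section 2.1.3 reports cases above normal people, not differences between types. This stands. A reader might infer that stage mix is known to differ strongly between the enrolled types, or that unequal stage mix alone makes the tests misleading. The protocol does not support the first, and the same-mix condition together with the formula in step 1 rules out the second.

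2. *Section 3.1.2 asks only for a correlation, under an exploratory heading.* An unadjusted comparison answers that question, and rejecting when the overall levels differ is then correct. This stands for a purely descriptive reading. It does not carry over to Objective 2, which wants separate statements on tumour type and on progression.

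3. *Pooling is inferred.* The trend test appears under subgroup correlation, and a statistical analysis plan that is not shown might stratify it. That is possible. But the protocol names the tests, states no second factor, and fixes the type comparison as one-way.

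4. *The large percentages come from one extreme stage mix.* This stands, which is why the range is shown. At a quarter of that spread the type test is barely affected.

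5. *A single model with one ordinal stage slope would impose the same trend on every tumour type.* This also stands, and it favours a type-stratified trend test over such a model.

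**Conclusion.** The point holds in conditional form. As named, the two one-factor tests cannot support separate conclusions on tumour type and disease progression if types differ in stage mix. The mechanism is certain; its size in this study is not. On the assumptions shown, the rate of misleading significance runs from barely above 5% to above 90% for the stage trend, and from about 6% to 85% for the type comparison. The percentages illustrate and do not forecast, and the upper ends need a strong stage-mix difference together with large differences in level.

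A reader might infer that the tests are invalid, or that the main result is in doubt. Neither follows. Each test is valid for the unadjusted association, and the primary case-control comparison and ROC analysis do not use them. This is an inexpensive improvement to a secondary analysis that should be made.

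**What to change.** In secondary analysis 1 of section 5.3:

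- Make the stage analysis a Cuzick-type trend test stratified by tumour type.
- Make the tumour-type comparison a linear model on the log- or rank-transformed level, with type as the factor of interest and stage entered as categories.
- Report the type-by-stage table of case numbers, so that readers can see how far the two factors overlap.
- Keep the pooled Cuzick and one-way tests as descriptive results.

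Only analysis wording changes: the planned tests already need type and stage for each case. The cost is a small loss of power (step 5) and a few degrees of freedom. Cases without a TNM stage drop out of both analyses, and types with few cases or nearly all cases in one stage contribute little to the stratified trend.

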Succinylation modification, as a widely existing post-translational modification of proteins, has potential biomarker value in malignant solid tumors. Besides tumors, existing studies have shown that some diseases (such as inflammatory diseases, infectious diseases, metabolic diseases, cardiovascular diseases, neuro-psychological diseases, etc.) have certain correlations with non-histone succinylation modification. The role of histone succinylation modification in other diseases is currently lacking in relevant clinical research evidence and awaits further exploration in this study. Therefore, this research focuses on malignant solid tumors, not only filling the knowledge gap in this field but also laying the foundation for future expansion to other diseases.

2.1.2 project objective

The core objective of the project is to systematically verify and establish the clinical

application value of serum histone succinylation modification as a novel, efficient and non-invasive pan-tumor biomarker.

Objective 1: Verify the potential of pan-tumor screening: Through large-scale case-control studies, it is clearly confirmed that there are significant differences in histone succinylation levels in serum between patients with malignant solid tumors and healthy individuals, thereby providing a solid evidence-based basis for developing it into a blood-based early screening tool suitable for multiple tumor types.

Objective 2: Exploring clinical application scenarios: The project will conduct an in-depth analysis of the association between serum histone succinylation levels and different types of tumors as well as different tumor stages, and evaluate its ability to distinguish tumor types and reflect disease progression. Meanwhile, analyze its correlation with therapeutic effects (changes in levels before and after surgery, radiotherapy, and systemic treatment) and clinicopathological characteristics, and explore its application prospects in dynamic monitoring of therapeutic effects and prognosis assessment.

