5.2 Research design process

5.2.1 Study the specific implementation process

1. Phase One: Screening and enrolling the population

- i. Conduct ethical reviews and clinical research protocol reviews for the project;
- ii. It is planned to select 500 patients with malignant solid tumors, collect their basic information and sign the "Informed Consent Form".
- iii: It is planned to select 500 healthy subjects and collect basic information.

2. Phase Two: Collect blood samples for serum histone succinylation detection

[figure not shown]
Blood samples were collected from all 500 enrolled individuals and 500 healthy subjects who met the requirements for serum histone succinylation detection.

3. Phase Three: Statistical analysis of Screening Results

- i. Western blot was used to evaluate the differences in serum histone succinylation between malignant solid tumors and healthy individuals to verify its early screening value.

ii. Statistically analyze the correlation between serum histone succinylation and tumor efficacy (including surgical treatment, radiotherapy, and systemic therapy) as well as clinicopathology. The therapeutic effect was evaluated using RECIST1.1 criteria.

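### The protocol describes its therapeutic-effect objective in two ways, and the only test that 5.3 names for it contains no response data

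*Protocol*

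**What the plan says.** Four places in the protocol describe what is to be learned about treatment.

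- Section 2.1.2, Objective 2: "analyze its correlation with therapeutic effects (changes in levels before and after surgery, radiotherapy, and systemic treatment". The parenthesis equates therapeutic effect with a change in the marker itself.
- Section 3.1.2, secondary objective: "statistically analyze the correlation between histone succinylation in serum and therapeutic effects", covering surgery, radiotherapy and systemic therapy. It does not repeat that gloss.
- Section 3.2, evaluation index: "the predictive value of the Youden index (early diagnosis, therapeutic effect evaluation and prognosis". Predictive value is thus meant to extend to the evaluation of treatment.
- Section 5.2.1, Phase Three, item ii: "Statistically analyze the correlation between serum histone succinylation and tumor efficacy (including surgical treatment, radiotherapy, and systemic therapy) as well as clinicopathology". The next sentence fixes the measure: "The therapeutic effect was evaluated using RECIST1.1 criteria".

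Section 5.3, secondary analysis 2, then gives the method: "The level changes before and after treatment were evaluated using paired t-test", with the Wilcoxon signed-rank test as the alternative. Neither RECIST nor tumour response is mentioned anywhere in 5.3.

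**The concern.** A correlation with therapeutic effect needs two variables per patient: the marker (or its change) and a measure of effect. The paired test uses only the marker, measured twice. If 5.3 is followed as written, RECIST assessments will be collected but no named analysis will use them, and the objective in 3.1.2 and 5.2.1 will have no result.

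Two situations show what is at stake. A shift that treatment causes in all patients, whether or not the tumour responds, gives a significant paired test and says nothing about response. A marker that falls in responders and rises in non-responders can give a null paired test although it does carry information about response.

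**Working it through.** **1. Does another analysis in 5.3 fill the gap?**

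| Analysis in 5.3 | What it relates | Uses response? |
|---|---|---|
| Group comparison, ROC, Youden cut-off | marker v case/control status | no |
| ANOVA / Kruskal-Wallis | marker v tumour type | no |
| Cuzick trend | marker v TNM stage | no |
| Paired t / Wilcoxon signed-rank | marker before v after treatment | no |
| Cox model, Kaplan-Meier | baseline marker v survival | no; baseline level, not change |
| Logistic model, DeLong, decision curve | outcome not named | none stated |

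None does.

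**2. Is there a figure in the plan to reproduce?** No. The only sample-size statement (d = 1.2, 10% dropout, 500 per group) concerns cases against controls. The protocol gives no number of patients, response rate or SD for the therapeutic-effect analysis.

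**3. Illustration under assumed inputs.** From the protocol: alpha 0.05 (sidedness not stated; two-sided used here), and an upper limit of 500 × 0.9 = 450 treated patients. Assumed: N = 100, 150 or 450; response rate p = 0.3 or 0.5; SD of change = 1 within each response group. There were 3,000 simulated trials per setting, comparing a one-sample t-test of the change (equivalent to the paired test) with a two-sample t-test of the change by response.

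Approximate noncentralities:
- paired test: mean change × √N / SD
- responder comparison: difference × √(N·p·(1−p)) / SD

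*Scenario A: a fall of 0.5 SD in everyone, unrelated to response.* The paired noncentrality is 0.5 × √100 = 5.0 at N = 100 and 0.5 × √450 = 10.6 at N = 450. For the responder comparison it is 0.

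*Scenario B: mean change 0, responders and non-responders 0.5 SD apart.* The paired noncentrality is 0. For the responder comparison:
- N = 100: 0.5 × √21 = 2.29 (p = 0.3) and 0.5 × √25 = 2.50 (p = 0.5)
- N = 150: 0.5 × √31.5 = 2.81 and 0.5 × √37.5 = 3.06
- N = 450: 0.5 × √94.5 = 4.86 and 0.5 × √112.5 = 5.30

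In B the AUC of change for response is Φ(0.5/√2) = 0.64; in A it is 0.50.

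Simulated rejection rates (ranges are over the two response rates):

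| N | A: paired | A: responder | B: paired | B: responder |
|---|---|---|---|---|
| 100 | 99.8% | 4.8–5.4% | 4.5–4.8% | 62–70% |
| 150 | 100% | 4.8–5.7% | 4.7–5.1% | 78–85% |
| 450 | 100% | 5.0–5.1% | 5.3% | 99.8–99.9% |

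The simulated rates agree with the noncentralities.

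**The case against.** A reader might infer that the protocol never links the marker to RECIST response and that its efficacy objective is wholly unanswered. The text does not support that.

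- Objective 2 in 2.1.2 glosses therapeutic effect as before/after level changes. On that wording the paired test is the analysis described. This stands; the fault is that 3.1.2 and 5.2.1 describe something else.
- Section 5.2.1 does commit to a correlation with efficacy and names RECIST 1.1 for it. Section 5.3 does not say that the paired test replaces this commitment or is the only efficacy analysis. The choice of test could be left to a statistical analysis plan, which is not at hand. This stands in part: the protocol did not leave the method open. It named one under this heading, and that one cannot deliver what 5.2.1 promises. A plan that follows 5.3 would inherit the gap.

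A reader might also infer that a significant paired test would be reported as evidence of efficacy, or a null one as showing the marker uninformative. No section contains such a reporting rule, so this is a risk and not a stated consequence.

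The illustration has limits too. Its inputs are assumed, and in scenario B the changes cancel by construction, so the paired test's 5% is built in. It demonstrates the logic and does not estimate this trial's loss.

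**Conclusion.** The concern holds as a mismatch within the protocol. Sections 3.1.2 and 5.2.1 set an association with RECIST-measured effect, 2.1.2 sets a before/after change, and the single method in 5.3 serves only the latter. Because a paired test contains no response data, its result is uninformative about association with response whatever inputs are chosen; the simulated rates only show how far the two questions can diverge.

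The weight is moderate. A secondary objective is left without an analysis that can answer it, while the primary diagnostic comparison does not depend on this.

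**What to change.** In 5.3, keep the paired test as a description of change within each treatment modality. Add, as the efficacy analysis, a baseline-adjusted comparison of marker change across RECIST 1.1 categories in systemic-therapy and chemoradiotherapy/radiotherapy patients with evaluable disease, with treatment modality as a covariate. Responder versus non-responder and an ordinal trend over categories are both defensible; one should be chosen in advance.

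Pre-specify one post-treatment sample per modality. The table in 5.2.3 offers more than one: as extracted, cycles 3 and 5 for systemic treatment, and end of treatment or four to six weeks later for radiotherapy/chemoradiotherapy. The RECIST assessment paired with that sample should also be named, since the visible text gives no imaging schedule.

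For surgical patients, sampled on days 1 to 3 and around discharge, state that only the before/after change is described and no association with response is claimed. They generally have no evaluable lesion after resection. Align 2.1.2, 3.1.2 and 5.2.1 with this wording.

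The cost is protocol wording, one extra analysis of data already planned, fewer patients in that analysis than in the whole case group, and a narrower efficacy claim that no longer covers surgery.

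### Secondary analysis 2 uses a two-point paired test on three-sample data, which can overstate a fall in the marker if patients whose marker is rising miss the later sample

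*Protocol*

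**What the plan says.** The blood collection table (section 5.2.3) gives each treated group a sample in the week before treatment and two later ones:

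- Systemic treatment (row "Cancer patients are receiving systemic treatment"): two later cycles. The columns suggest cycles 3 and 5, but the table layout is damaged in the text at hand.
- Radical radiotherapy or chemoradiotherapy: at the end of treatment, then "Four to six weeks after the completion of radiotherapy/chemoradiotherapy".
- Surgery: days 1 to 3 after the operation, then "Postoperative discharge day/the day before discharge".

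Section 5.3, Secondary analysis 2, fixes the method: levels before treatment are compared with levels after it by "paired t-test /Wilcoxon signed-rank test". It does not say which of the two later samples counts as the one after treatment, and it names no model for repeated samples. The only rule for missing data is "multiple imputation (MICE) for filling <5% of missing covariates", which does not reach the marker itself. The only dropout figure in the protocol is in the sample-size sentence: "considering a 10% dropout rate".

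Section 2.2 describes a single blood draw, whereas section 5.2.3 schedules three for treated patients. The two sections must be reconciled. This point takes the table as the plan.

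**The concern.** A paired test estimates the mean change among patients who have both samples. That equals the mean change among all treated patients only if absence of the later sample is unrelated to the course of the marker.

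The protocol's own hypothesis makes this doubtful. Objective 2 (section 2.1.2) expects the level to reflect progression and to track treatment effect. If that is right, patients who progress or stop before the later sample tend to be those whose marker is rising. Those who remain then show a fall that is partly a product of who is still being sampled.

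Treatment effect is a declared secondary objective (section 3.1.2), so such a fall could be reported as evidence that the marker is useful for monitoring.

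**Working it through.** **Plan's own figure.** There is none to reproduce. The sample-size sentence concerns cases against controls, and no variance, correlation or missingness is given for the marker over time. Everything below is therefore an assumption, except the 10% dropout and the 0.05 test level (taken as two-sided).

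**Main model.**
- 160 patients in one modality, roughly a third of 500 (500/3 = 167).
- Between-patient SD 0.8 and error SD 0.6. Total SD = √(0.64 + 0.36) = 1.0, so results read as SD units.
- 40% of patients change by −0.5 and 60% by about +0.33. Mean change = 0.4 × (−0.5) + 0.6 × 0.33 ≈ 0.
- Half or all of the change is present at sample 2.
- The log-odds of missing sample 3 rise by 1 to 2 per unit of observed change at sample 2, with the overall missing fraction set at 10% or 28%.

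**Formula.** With B the false fall among complete pairs, s the SD of their change and n the pairs left, let z = B/(s/√n). The rejection rate is Φ(z − 1.96) + Φ(−z − 1.96). B and s come from simulation.

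| Missing | n | Case | B | s | z | Rejection |
|---|---|---|---|---|---|---|
| 10% | 144 | mildest | 0.044 | 0.936 | 0.56 | 9% |
| 10% | 144 | strongest | 0.076 | 0.921 | 0.99 | 17% (18% with B rounded to 0.08) |
| 28% | 115.2 | mildest | 0.112 | 0.926 | 1.30 | 25% |
| 28% | 115.2 | strongest | 0.189 | 0.904 | 2.24 | 61% |

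**Comparison of the first two samples.** In this model sample 2 is never missing, so the paired test from baseline to sample 2 keeps its 5% level. Only the last comparison is affected.

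**Models using all three samples, same data.** Likelihood estimation with unstructured covariance gives a change of about 0.00 throughout. A patient random intercept alone leaves about −0.02 to −0.04 at 28% missing, because it assumes equal correlation between all visits, whereas samples 2 and 3 share the response effect.

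**Second model as a check.** Three normal values with SD 1 and correlation 0.5, 167 patients, no true change, odds ratio 2 to 3 per SD of change for missing the third sample:

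| Missingness depends on | Missing | Complete-pair bias (SD) | Rejection | Bias, all-samples model (SD) |
|---|---|---|---|---|
| nothing (random) | 10–30% | 0 | 5% | 0 |
| observed change at sample 2 | 10% | −0.03 to −0.05 | 7–9% | about 0 |
| observed change at sample 2 | 30% | −0.10 to −0.13 | 18–31% | about 0 |
| unseen change at sample 3 | 10% | −0.07 to −0.10 | 13–25% | −0.05 to −0.07 |
| unseen change at sample 3 | 30% | −0.19 to −0.27 | 57–90% | −0.13 to −0.19 |

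The direction agrees with the main model. When missingness depends on the unseen value, the all-samples model keeps about two thirds of the bias.

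**The case against.** The strongest reply is that handling of missing follow-up values and the choice of time point are commonly left to a statistical analysis plan, which may exist. The protocol never states that only complete pairs are used, and a before-and-after change is a legitimate secondary quantity. Each later sample could be paired with baseline, and section 5.3 already applies false-discovery control to multiple comparisons. The document also has no evidence that samples will be missing for reasons linked to the marker.

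Part of this stands. The restriction to complete pairs is inferred from the tests named, and the bias is conditional. But the protocol does not leave the method open: it names a two-point test for a three-sample schedule, and that test cannot use a patient who lacks the later value. Pairing each later sample with baseline does not cure this, nor does false-discovery control.

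Two stronger readings are tempting. A reader might infer that a false positive in some 40% of trials is to be expected. That needs about 28% missing and a particular strength of dropout, neither of which is in the protocol; at its own 10% the figure is 9 to 18%. That 10% does belong to the sample-size statement, and loss at a later cycle could be higher, but the documents do not say. A reader might also infer that every treated group is affected. In surgery both later samples fall by discharge, so progression or stopping treatment hardly enters.

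**Conclusion.** The point holds as a conditional one. The two-point paired test in Secondary analysis 2 does not fit the sampling schedule. It overstates the fall at the later systemic-treatment sample, and at the radiotherapy follow-up visit, if patients with a rising marker are more likely to be missing there.

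Under the main model the overstatement is modest at the protocol's 10% dropout and material at 28% missing. The size rests wholly on assumed variance, response mix and dropout strength; only the direction is common to all the informative-missingness scenarios examined. If samples are missing at random with respect to the marker, there is no bias.

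This is a secondary analysis. The comparison of cases with controls and the diagnostic accuracy results do not depend on it. It should be changed because the risk runs in the favourable direction and the remedy is cheap.

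**What to change.** In section 5.3, Secondary analysis 2, replace the paired test as the main method. Within each treatment modality, fit a repeated-measures model to all scheduled samples:

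- Outcome: log level.
- Time as a category.
- Unstructured within-patient covariance, rather than a random intercept alone.
- Tumour type and stage as covariates.

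Report the change from baseline at each later time, which also settles which sample counts as the one after treatment. Keep the paired t-test or Wilcoxon test as supportive.

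The model relies on missingness depending only on observed values. This is weaker than what the paired test needs, but it removes the bias only in part if missingness depends on the unseen value. Add a short sensitivity analysis for that case, and report the number of samples missing at each time by modality.

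The cost is a change of wording, a standard model in R (the software already named) and a little more analysis work. No extra samples or patients are needed.
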